4.6.4 Removal of Device	17
4.7 Examination Requirements	18
4.8 Enrollment, Randomization, Masking and Unmasking	20
5 Safety Monitoring and Reporting	22
5.1 Safety Monitoring Committee	22
5.2 Adverse Experience Reporting	22
5.3 Obligations of Site Investigators	22
5.4 Obligations of Study Sponsor	25
5.5 Adverse Events Defined	25

5.6	Withdrawal Criteria	27
6	Statistical Considerations	28
6.1	Description of Trial	28
6.2	Analysis Populations	28
6.3	Efficacy and Safety Variables	28
6.4	Sample Size Rationale	29
6.5	Statistical Analysis Plan	29
6.6	Interim Monitoring	29
7	Human Participant Protection	29
8	Study Risk and Precautions	31
8.1	NT-501 Device Implant and Sham Surgery	31
8.2	CNTF and CNTF Producing Cells	31
8.3	Dilation and Anesthetic Drops	31
8.4	IOP Examination and ERG	31
9	Confidentiality and Access to Source Documents and Data	31
10	Summary of GCP Compliance	32
10.1	Investigator Responsibilities	32
	Institutional Review Board	33
	Review of Protocol, Consent and Recruitment Materials	33
10.2	Data Handling and Record Keeping	34
10.3	Protocol Amendments	34
10.4	Monitoring Plan	35
10.5	Retention of Records	36
11	Certifications and Training Requirements	36
11.1	Certification for AOSLO Image Acquisition and Analysis	36
11.2	Certification for Humphrey Visual Field Testing	38
11.3	Professional Licensure	38
12	References	39
13	Appendix: NT-501 Implant Accessories: Surgical Tool Information	43

Protocol Summary

Protocol Title:	Photoreceptor Structure in a Phase 2 Study of Encapsulated Human NTC-201 Cell Implants Releasing Ciliary Neurotrophic Factor (CNTF) for Participants with Retinitis Pigmentosa Using Rates of Change in Cone Spacing and Density as the Primary Outcome
Protocol Designation:	CNTF/UCSF
Test Article:	NT-501 Encapsulated cell intraocular implant; releasing CNTF.
Primary Endpoint(s):	The primary efficacy variable is the rate of change in cone spacing and cone density from baseline to 30 months.
Secondary Endpoints(s):	Secondary efficacy variables will include: mean change from baseline value in Humphrey Visual Field Sensitivity (VFS) from baseline to 24 months, mean change in “5-point” VFS from baseline to 24 months (using the 5 retinal points with greatest average change), mean change from baseline in Best Corrected Visual Acuity (BCVA) at 12, 18, 24, 30 and 36 months, and changes in ERG, Optical Coherence Tomography (OCT), clinical grades of inflammation (anterior chamber cell and vitreous haze grades), and vision-related quality of life (NEI-VFQ25) at each visit.
Safety Endpoint(s):	Safety variables will include the incidence of adverse events, changes in vital signs, marked changes in clinical laboratory data, ECG abnormalities, and findings during physical examinations through 36 months
# of Clinical Sites:	This is a single investigator study; Retinal Degenerations Clinic at the University of California, San Francisco
# of Study Subjects:	Approximately 30
Inclusion Criteria:	
1. Participant must be between 18 and 55 years of age.2. Participant must have a diagnosis of retinitis pigmentosa or Usher syndrome type 2 or 3.3. Participant must understand and sign the protocol informed consent. If the participant’s vision is impaired to the point where he/she cannot read the informed consent document, the document will be read to the participant in its entirety.4. Best-corrected visual acuity must be no worse than 20/63 (at least 59 letters).5. Participants must have clear natural lenses.6. Participants must have less than 6 diopters myopia.7. Participants must be medically able to undergo ophthalmic surgery for the NT-501 device insertion and able to undergo all assessments and tests associated with the protocol.

8. Females of childbearing potential (women with last menses \leq 1 year prior to screening) must agree to use an effective form of birth control from study onset until they complete the study.
9. Participants must have reproducible baseline AOSLO image montages at 2 baseline imaging sessions with quality suitable to identify a minimum of 7 regions of interest (ROIs) at which reliable cone spacing and/or density measures can be made over the central 5.7 degrees.
10. Participants must have interocular symmetry of disease severity as measured by cone spacing, with a difference of less than 2 standard deviations in average cone spacing z-scores at the selected ROIs between the 2 eyes.
11. Participant's clinical diagnosis must be consistent with retinal degeneration in the set of retinitis pigmentosa (RP) dystrophies characterized by the following features:
 - a) clinical evidence of progressive photoreceptor cell dysfunction and degeneration of the outer retina;
 - b) intraretinal 'bone-spicule'-like pigment observed on clinical examination;
 - c) peripheral visual field constriction documented on standard testing;
 - d) symptomatic night blindness;
 - e) reduction of both rod and cone electroretinogram (ERG) responses.

For purposes of this study, individuals diagnosed with Retinitis Pigmentosa or Usher Syndrome Type 2 or Type 3 (without profound deafness or cochlear implants) who meet the inclusion criteria will be considered as potential candidates for this study. A maximum of 4 Usher Syndrome Type 2 or Type 3 participants may be enrolled in this trial.

Exclusion Criteria:

1. Participant is medically unable to comply with study procedures or follow-up visits.
2. Participant who has any of the following lens opacities: cortical opacity $>$ standard 3, posterior subcapsular opacity $>$ standard 3, or a nuclear opacity $>$ standard 3 as measured on the AREDS clinical lens grading system; or participant is pseudophakic or aphakic.
3. Participant has history of corneal opacification or lack of optical clarity.
4. Participant has undergone LASIK surgery or other refractive surgery for either eye.
5. Participant has nystagmus.
6. Participant has greater than 6 diopters myopia.
7. Participant has cystoid macular edema with cysts present within 4 degrees of the foveal center.
8. Participant has fewer than 7 ROIs present on 2 baseline AOSLO image montages.
9. Participant has retinal vascular disease such as diabetic retinopathy or prior retinal vascular occlusive disease.

10. Participant has chronic requirement (e.g., ≥ 4 weeks at a time) for ocular medications or has disease(s) that in the judgment of the examining physician are vision threatening, toxic to the lens, retina, or optic nerve or may affect the primary outcome.
11. Participant has a requirement of acyclovir and/or related products during study duration. To be eligible for this study, the participant must discontinue use of these products prior to enrollment and must not continue with the products until after they have completed the study.
12. Participant is receiving systemic steroids or other immunosuppressive medications.
13. Participant is currently participating in or has participated in any other clinical trial of a drug by ocular or systemic administration within the last 6 months.
14. Participant has previous exposure to an intra-ocular device or implant into the eye (excluding intra-ocular lens).
15. Participant has uveitis or other retinal inflammatory disease.
16. Participant has a history of myocardial infarction within the last 12 months.
17. Participant is pregnant or lactating.
18. Participant is considered immunodeficient or has a known history of HIV. A laboratory test for HIV will be performed, and a positive result is also an exclusion criterion.
19. Participant with a history of ocular herpes zoster.
20. Participant is on chemotherapy.
21. Participant has a history of malignancy, except study participant with cancer treated successfully ≥ 5 years prior to inclusion in the trial.
22. Participant with severe hearing disabilities in both ears.
23. Participant who has been diagnosed and treated for amblyopia as an infant.
24. Participant who, in the opinion of the study doctor, will not be a good study subject.

Visit Schedule of events and participant procedures is provided in Table 1

Table 1: Visit Schedule

SCHEDULED VISIT WEEK	Baseline 1 (Screening) ¹	Baseline 2 (Screening) ¹	Baseline 3 (<4 days pre-op) ²	Implant Surgery	1 Day Post-Op	1 Week (+ 3 days)	1 Month (+ 3 days)	6 Months (+7 days)	12 months (+14 days)	18 Months - (+14 days)	24 Months - (+14 days)	30 Months - (+21 days)	36 Months - (+21 days)
GENERAL ASSESSMENTS													
Informed consent	X												
Medical history, brief PE, and systems review	X				X	X	X	X	X	X	X	X	X
Vital signs (BP, respiratory rate, temperature)	X		X ³		X	X	X	X	X	X	X	X	X
ECG			X ³										
AE assessment					X	X	X	X	X	X	X	X	X
Implant site clinical examination					X	X	X	X	X	X	X	X	X
NEI-VFQ25 questionnaire	X						X	X	X	X	X	X	X
VISUAL SYSTEM EXAMS													
Manifest Refraction	X						X	X	X	X	X	X	X
Best Corrected Visual Acuity, IOP	X	X			X	X	X	X	X	X	X	X	X
Slit lamp exam and dilated fundus exam	X	X			X	X	X	X	X	X	X	X	X
AOSLO	X ⁵	X ⁵					X	X	X	X	X	X	X
Axial length, anterior chamber depth, corneal curvature measurement [a-scan]	X							X		X	X	X	X
Humphrey 10-2 Visual Field	X ⁴						X	X	X	X	X	X	X
Dark Adapted Fundus-Guided Microperimetry	X ⁴						X	X	X	X	X	X	X
Infrared Fundus Photographs	X ⁴						X	X	X	X	X	X	X
Spectral domain OCT	X ⁴						X	X	X	X	X	X	X
ERG			X ⁴					X		X			
STUDY THERAPY													
Implant Surgery					X								
LABORATORY													
Serum chemistry , hematology, urinalysis			X ³						X		X		X
Urine Pregnancy ⁶			X ³						X		X		X
HIV testing			X ³										
Genetic testing through eyeGENE			X ⁷										
Serum for antibody/CNTF concentration			X						X		X	X	X

¹ Baseline 1 Screening will occur within 7 weeks of implant surgery; Baseline 2 Screening will occur within 4 weeks of Baseline 1.

² Baseline 3 will occur < 4 days prior to implant surgery

³ ECG and pre-op laboratory testing should be performed within the timeframe mandated by the OR.

⁴ Measurement or exams should be taken at any point within 7 weeks preceding implant surgery.

⁵ Measurement at Baseline 1 must establish a minimum of 7 ROI's; measurement at Baseline 2 must verify a minimum of 7 of the previously established ROI's for measurement throughout the study period.

⁶ Urine pregnancy test will only be performed on premenopausal women.

⁷ Genetic testing will be offered to patients with diseases for which eyeGENE offers testing. Separate consent is required and patients can refuse to submit blood for genetic testing but still participate in the present study.

Photoreceptor Structure in a Phase 2 Study of Encapsulated Human NTC-201 Cell Implants Releasing Ciliary Neurotrophic Factor (CNTF) for Participants with Retinitis Pigmentosa Using Rates of Change in Cone Spacing and Density as the Primary Outcome

1 Background and Rationale

Retinitis Pigmentosa (RP) is a group of hereditary disorders whose common feature is a progressive deterioration of the rod and cone photoreceptors in the retina, which results in the reduction and loss of both peripheral and central vision. Histopathologic studies in naturally occurring and genetically engineered animal models of photoreceptor dysfunction and death in the condition termed retinitis pigmentosa (RP) have indicated the promise of ciliary neurotrophic factor (CNTF) as an effective therapeutic agent for reducing photoreceptor loss associated with degeneration of the cells of the outer retina. CNTF is one of several neurotrophic factors that are produced endogenously by neurons or supporting glial cells and has been demonstrated to be highly effective in retarding photoreceptor neuron loss in 12 animal RP models with various forms of retinal degeneration.

One of the major challenges in the treatment of RP is to deliver therapeutic macro-molecules such as CNTF to the retina. The blood-retinal barrier effectively prevents the passage of large therapeutic molecules from the bloodstream into the tissues of the eye thus limiting systemic treatment approaches. Neurotech developed a form of encapsulated cell technology (ECT) specifically to overcome this challenge. This technology enables the controlled, continuous and long-term delivery of therapeutic macro-molecules, including a wide variety of neurotrophic factors and other proteins and compounds, directly into the vitreous cavity inside the eye.

Due to RP's slow progression and standard clinical imaging techniques that have, until recently, been unable to visualize individual photoreceptors due to optical imperfections in living eyes, it has been challenging to evaluate CNTF's potential to treat RP. Natural history studies of retinal degeneration predict that significant changes in visual function may be measured reliably only after greater than 7 years, suggesting that significant photoreceptor loss is necessary before changes in visual function can be measured reliably (Fishman et al, 2007; Grover et al, 1997; Iannaccone et al, 2004). However, adaptive optics (AO) ophthalmoscopy, including adaptive

optics scanning laser ophthalmoscopy (AOSLO), can produce images of individual cone photoreceptors non-invasively in living eyes (Liang et al, 1997; Roorda et al, 2002; Zhang et al, 2006). Direct visualization of cones allows comparison of cone spacing and density, and in ideal situations, tracking of individual cones longitudinally. Cone spacing and density have been used to characterize normal eyes and eyes with retinal degeneration (Choi et al, 2006; [name] et al, 2007; Rossi et al, 2010). In addition, dark-adapted fundus-guided microperimetry has been used to study visual function reliably and provides insight into the function of both rods and cones in the macula of patients with retinal degeneration (Crossland et al, 2010).

Preliminary studies using AOSLO to image cones in patients with retinal degenerations showed reduced rates of cone loss in eyes treated with CNTF compared to contralateral eyes that received sham treatment over 24-32 months, despite no significant changes in visual acuity or visual field (Talcott et al, 2010). These studies suggest that CNTF may be effective in slowing the rate of photoreceptor loss in eyes with retinitis pigmentosa and Usher syndrome, but that measures of visual function including visual acuity and visual field sensitivity are not sufficiently sensitive to identify a treatment effect over 24 months.

2 Scientific Rationale

2.1 Encapsulated Cell Technology

[figure not shown]
Encapsulated cell implants (NT-501) consist of cells encapsulated within supportive matrices and surrounded by a semi-permeable polymer membrane. The NT-501 implants consist of encapsulated NTC-201 cells. The NTC-201 cells¹, which produce ciliary neurotrophic factor (CNTF) in the NT-501 device, are derived by genetically modifying the NTC-200 cells using a proprietary plasmid vector containing the CNTF gene. The NTC-200 cells are derived from a human retinal pigment epithelial cell line, ARPE-19 (ATCC # CRL-2302). This cell line is diploid, non-tumorigenic and meets established criteria for safety and freedom from microbial contaminants and adventitious viruses (Investigational New Drug Application BB-IND-10931).

Two implant dosage forms, high (NT-501-6A.02) and low (NT-501-10.02) CNTF-secreting implants, were developed and employed in phase 1 and phase 2 studies to allow for the

¹ A spontaneously immortalized human retinal pigment epithelial line derived from the ARPE-19 line (ATCC No. CRL-2302).

evaluation of different CNTF dosing regimens and their respective safety profiles in patients with RP. Implants appeared identical, but differed in that they were loaded with either a high output (NTC-201-6A) or low output (NTC-201-10) CNTF-secreting cell line. The CNTF-specific productivity rate of the NTC-201-6A cell line is 800 ng CNTF per 1×10^6 cells per day. The NTC-201-6A cells are used to produce the CNTF secreting NT-501 implant that releases CNTF at 20 ng/day. The NTC-201-10 cell line is a lower output line at 250 ng CNTF per 1×10^6 cells per day are used to produce the CNTF secreting NT-501 implant that releases CNTF at ~ 5 ng/day.

Figure 1 *Schematic Representation of the NT-501 Implants*

2.2 Rationale of ECT in Participants with RP

Currently, there are no treatments available for retinal degenerative disorders, and the clinical course for RP is very poor. RP symptoms usually manifest in patients between the ages of 7-30 and the rate of progression varies among them. Most RP patients are legally blind by age 40. It has been hypothesized (Seiving et al, 2006) that CNTF implants improved the visual acuity of some of these participants who had both advanced RP and atrophic macular degeneration.

2.3 Rationale for Use of Sham Surgery

This Phase 2 study will explore the effect on cone spacing and cone density over a 24-month period of CNTF release by the NT-501 intravitreal device to establish whether CNTF delivered in this manner can improve cone photoreceptor survival or lessen the decline in cone density relative to the contralateral control eye. Measures of change in visual acuity, visual field sensitivity and disease modification will be collected over a total of 24 months as secondary

outcomes. Given this observation period to reach the primary outcome and the relatively small, absolute magnitude of improvement expected, a control sham treatment with minimal risk to the fellow eye is justified to qualify the chance that any observed differences are a result of a participant effort rather than from the treatment itself.

2.4 Rationale for Excluding Participants Under 18 or Above 55 Years of Age

The age limits were selected to maximize the homogeneity of the RP population under study. Participants younger than 18 or older than 55 may have a different clinical course of disease.

3 Study Objectives

The objective of this study is to investigate whether CNTF improves or lessens the rate of cone photoreceptor loss, measured as increased cone spacing or decreased cone density, relative to the fellow control eye in participants with Retinitis Pigmentosa and Usher Syndrome types 2 and 3.

4 Study Design and Methods

This is a prospective, randomized, double-masked, sham-controlled trial of approximately 30 study participants with reduced vision in both eyes due to RP and Usher Syndrome types 2 and 3. This trial will be conducted at the Retinal Degenerations Clinic at the University of California, San Francisco. The surgeon designated by the Principal Investigator will not be masked as to which eye received the implant and which eye received the sham. The participants and the technicians will be masked regarding the sham versus implant eye.

All participants will receive the implant after successfully completing baseline examinations during which participant's eligibility to participate in the trial will be determined (see section 4.6.1).

Although implants containing the “high output” CNTF-secreting cell line are the intent of the study, a cohort of “low output” implants will also be studied: The initial 9 participants will receive the high output implant; the subsequent 6 participants will receive the “low output” implant, and the remainder of subjects will receive the “high output” implant.

Initial implantation of the investigational devices will be staggered over a 3-month period in order to permit a review of patient safety data by the SMC. The 3-month staggered enrollment

will occur as follows. Here, references to days, weeks and months are relative only to the first surgical procedure:

- The first patient will undergo surgical implantation of the investigational product on day 1 of week 1.
- The one day, one week and one month post implant safety findings for the first patient will be forwarded to the Chairman of the SMC for review of the safety findings. Communicating the outcome of the SMC review will be accomplished prior to week 5.
- Assuming a recommendation to continue enrollment results from the SMC's review of safety data (up to one month post implant), the second patient will undergo surgical implantation of the investigational product during day's 1 – 5 of week 5.
- The 2-month post implant safety data for patients 1 and the one-month post-implant safety data for patient 2 will be supplied to the chairman of the SMC at the beginning of week 9.

The SMC's recommendation was to continue enrollment following the SMC review of safety data (up to two month post implant). The remaining patients will undergo surgical implantation of the investigational product in accordance with enrollment.

Devices will not be explanted except in instances where it is medically advised due to an adverse event. An examination for safety will occur one day following surgical implant and periodically thereafter.

All participants will be followed clinically for 30 months.

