4.1 Outcomes

Primary Outcome:

The primary outcome is rate of change in cone spacing and rate of change in cone density as determined using AOSLO images of regions of interest (ROIs) preselected at baseline in eyes treated with CNTF compared to contralateral eyes treated with sham surgery over 30 months. Cone spacing and density will be measured by 3 independent graders who will remain fully masked to the treatment assignment throughout the duration of the trial. We will compare rates of change in cone spacing and cone density between CNTF-treated and contralateral sham-treated eyes through 30-months using pooled linear regression.

Secondary Outcomes:

Secondary outcome measures will involve comparing rates of change in standardized measures of visual function between CNTF- and sham-treated eyes. Secondary outcomes will include the following functional and structural assessments: mean and median change in best spectacle-corrected visual acuity (BCVA) using the ETDRS protocol, changes in visual field sensitivity and foveal sensitivity in decibels (dB) using automated static perimetry using the Humphrey visual field 10-2 protocol and rod and cone-mediated fundus-guided microperimetry using a modified Nidek MP1, changes in thickness of the outer nuclear layer (ONL) and outer segment plus RPE (OS+) layer thickness as measured using spectral-domain optical coherence tomography (SD-OCT), and changes in full-field ERG scotopic and photopic standard a- and b-wave amplitudes and timing from baseline to 36 months. All parameters except full-field ERG will be measured at 6, 12, 18, 24, 30 and 36 months after implant surgery; standard full-field ERG will be performed according to ISCEV standards at baseline, 12, and 24 months.

Safety Outcomes:

Safety of the NT-501 ECT technology implant has been demonstrated in prior Phase 1 and Phase 2 trials of the implant. Separately from efficacy outcomes which demonstrate a reduction or increase in function, safety parameters will continue to be collected and assessed by the following outcomes (occurrence of these outcomes does not necessarily require explant):

- Rejection or extrusion of the NT-501 device.
- Protocol-related abnormal findings from serum chemistry, hematology, and urinalysis (those abnormal findings that are determined to be clinically significant by the Principal Investigator).

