6.1 Description of Trial

10 subjects will be enrolled into the study. Both eyes of each participant will be evaluated in this study. There are, thus, a minimum of 10 participants and a minimum of 20 eyes in the trial. One eye of each participant will be randomly assigned to receive CNTF, and the fellow eye will receive sham surgery. AOSLO montages will be acquired at baseline 1 covering the central 5.7 degrees to identify at least 7 ROIs where unambiguous cone mosaics are visualized. AOSLO images will be acquired at Baseline 2 within 1 month of Baseline 1 and focused on the ROIs. Humphrey visual field sensitivity of each eye will be measured at baseline, month 6, month 12, month 18, month 24 and month 30. The total score for the entire retina, averaged across replicates, will serve as the unit of analysis for baseline qualifications and efficacy outcomes. In addition, the 5 points of the visual field with the greatest change during treatment will serve as a key secondary efficacy variable. Pupil size will be recorded during HVF assessment.

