6.3 Efficacy and Safety Variables

The primary efficacy variable is the rate of change in cone spacing and cone density from baseline to 24 months. Secondary efficacy variables will include: mean change from baseline value in Humphrey Visual Field Sensitivity (VFS) from baseline to 24 months, mean change in “5-point” VFS from baseline to month 24 (using the 5 retinal points with greatest average change), mean change from baseline in Best Corrected Visual Acuity (BCVA) at 12, 18, and 24 months, and changes in ERG, Optical Coherence Tomography (OCT), clinical grades of

inflammation (anterior chamber cell and vitreous haze grades), and vision-related quality of life (NEI-VFQ25) at each visit.

The mean change in VFS will be calculated using the sum of all points at baseline and each follow-up visit. Likewise, the 5 points with greatest change from baseline will be selected for each patient based on the average score per point across replicates at baseline and at month 24; the mean of these 5 points will be used to compute the change from baseline in “5-point” VFS.

Safety variables will include the incidence of adverse events, changes in vital signs, marked changes in clinical laboratory data, ECG abnormalities, and findings during physical examinations.

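### The primary time point is 24, 30 or 36 months depending on the section, and protocol section 4 ends follow-up before the month-36 visit that the SAP tests

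*Protocol*

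**What the plan says.** **Primary time point.** The Protocol Summary states: "The primary efficacy variable is the rate of change in cone spacing and cone density from baseline to 30 months". Section 4.1 agrees, comparing CNTF-treated with "sham-treated eyes through 30-months using pooled linear regression". Section 6.3 repeats the Summary sentence with a different horizon: "The primary efficacy variable is the rate of change in cone spacing and cone density from baseline to 24 months". Section 6.4 describes the primary analysis over 24 months and calls that the study period. Section 2.3 also describes a 24-month exploration of cone spacing and density. SAP 7.5.1.1 labels the 36-month measurement as the primary outcome, marks it as required, and bases the primary hypothesis test on it.

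**Length of follow-up.** Section 4 of the Protocol says: "All participants will be followed clinically for 30 months". Section 6.1 says: "Humphrey visual field sensitivity of each eye will be measured at baseline, month 6, month 12, month 18, month 24 and month 30". Section 5.6 builds the withdrawal visit from the 30-month assessments, and section 6.2 judges cataract at 30 months. Table 1, on the other hand, ends with a 36-month visit that includes AOSLO and Humphrey fields. The secondary-outcome text in 4.1 says: "All parameters except full-field ERG will be measured at 6, 12, 18, 24, 30 and 36 months after implant surgery". The Summary safety endpoint covers "findings during physical examinations through 36 months". SAP 2.3.1 sets a 36-month study period.

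All of this is current text; none of it comes from a record of changes.

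**The concern.** The primary time point decides which result is confirmatory at the two-sided 0.05 level. The Protocol contradicts itself on it (24 or 30 months), and neither value is the SAP's 36. A result at any of the three could be presented as primary with a citation to one of the documents.

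The follow-up wording adds a practical risk. The SAP's primary test uses two time levels, baseline (the mean of two sessions) and final follow-up. The visit that falls after section 4's end of follow-up is therefore the one that supplies the whole post-baseline side of the test. A participant managed to section 4 would be complete under the Summary and 4.1, yet would have no observed primary value under the SAP.

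Masking hangs on the same date. Section 4.8 tells participants which eye was implanted when the study ends. If that is read as month 30, they would know before the month-36 acuity, visual field and questionnaire assessments, all of which depend on their responses. The AOSLO graders are masked separately, so the cone measurements are less exposed.

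**Working it through.** **Step 1. Set the sections side by side.**

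| Place | Primary time point | End of follow-up or last measurement |
|---|---|---|
| Protocol Summary | 30 months | safety to 36 months |
| Table 1 | not stated | 36 months |
| Protocol 2.3 | 24-month period | secondary outcomes over 24 months |
| Protocol 4 | not stated | 30 months |
| Protocol 4.1 | 30 months | secondary outcomes to 36 months |
| Protocol 5.6 | not stated | 30-month assessments at withdrawal |
| Protocol 6.1 | not stated | Humphrey fields to 30 months |
| Protocol 6.2 | not stated | cataract judged at 30 months |
| Protocol 6.3, 6.4 | 24 months | 6.4 calls 24 months the study period |
| SAP 2.3.1 | not stated | 36 months |
| SAP 7.5.1.1 | 36 months | 36 months |

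Spread of stated primary time points: 36 − 24 = 12 months.

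**Step 2. Size the follow-up gap.** 36 − 30 = 6 months, and 6/36 = 17% of the study period. The six-monthly AOSLO visits fall at 6, 12, 18, 24, 30 and 36 months, so one of six lies beyond month 30. In the SAP's primary test it is one of one, because no other post-baseline visit enters the change score.

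**Step 3. Check what the sample size is tied to.** SAP 3.1 gives a difference of 0.084 arcminutes over two years, a standard deviation of 0.11 for the two-year difference, 80% power, two-sided alpha 0.05 and 15% loss.

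- Standardised effect: 0.084/0.11 = 0.76.
- Normal approximation: n = ((1.96 + 0.84) × 0.11/0.084)² = 13.5, so 14.
- Exact paired t-test: n = 16 gives 81.4% power and n = 17 gives 84.0%.
- Loss to follow-up: 17/(1 − 0.15) = 20.

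The SAP states 17, or 20 after loss, so its figure reproduces to within one participant. It is explicitly a two-year calculation in arcminutes. The SAP's primary test is a 36-month change in z-scores, and the documents give no standard deviation for that quantity. The sizing therefore neither settles the primary time point nor gives the power of the 36-month test.

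**Step 4. Trace the consequence under each reading.**

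- *Table 1 is followed.* All visits to month 36 take place and nothing is lost. The protocol's primary comparison (24 or 30 months) still differs from the SAP's (36 months).
- *Some participants stop at month 30 under section 4.* Their month-36 values are missing, and SAP 7.6.2 imputes them, including where every region of an eye is missing.
- *Everyone stops at month 30.* There would be no month-36 values to which the regression-based imputation could be fitted, so the SAP's primary test could not be run as written.

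**The case against.** The best defence is that the SAP is clear. Version 2.0, dated April 2022, names month 36 as primary and required, and protocol 6.5 assigns the efficacy analysis to the SAP. Section 4.4 sends the site to Table 1, which contains the month-36 visit. At a single clinic working from that table, the visit will probably happen. This stands: a reader of the SAP alone knows which result is primary, and loss of data is the less likely outcome. It does not remove the conflict, because the Protocol gives two other primary time points and no text says which document prevails where they differ.

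The 6.1 visual field list also matters less than it looks. The Summary and 6.3 define the field-sensitivity endpoint at 24 months, which a list ending at month 30 covers. The list still contradicts Table 1 and 4.1.

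Three stronger readings are tempting, and the documents do not support them.

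- *The unsettled primary time point caused the 30-month follow-up text.* The two are consistent, but no passage states a cause. Incomplete updating of the text would explain both equally well.
- *Section 4 means the primary data will be missing and imputed.* That holds only for participants actually stopped at month 30, and Table 1 directs otherwise.
- *The expected effect can be scaled from two years to 30 or 36 months to measure the damage.* Section 6.4 implies 0.084/2 = 0.042 arcminutes per year. The protocol compares rates, so under a constant yearly effect the target is 0.042 per year at every horizon. The SAP tests z-scores. Scaled arcminute differences describe neither analysis.

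**Conclusion.** The concern holds as an inconsistency within the Protocol and between it and the SAP, and it should be corrected. The primary time point has three stated values spanning 12 months. Section 4 and the 6.1 list stop 6 months before the visit on which the SAP's primary test depends. Section 4 does match the 30-month primary endpoint in the Summary and 4.1. As a statement of follow-up for all participants, however, it conflicts with Table 1 and with the safety and secondary outcomes, whichever primary time point is chosen.

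What is at stake for certain is which result counts as confirmatory. Missing month-36 values and early unmasking are conditional risks: the first arises only if a participant is managed to section 4 instead of Table 1, the second only if the end of the study is read as month 30. The conclusion rests on comparing the texts, not on any modelling assumption. It does not imply that the sample size calculation is wrong on its own two-year terms in the SAP.

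**What to change.** - State one primary time point (36 months if the SAP governs) in the Protocol Summary, 2.3, 4.1, 6.3 and 6.4, matching SAP 7.5.1.1.
- Change clinical follow-up in section 4 to 36 months and add month 36 to the Humphrey list in 6.1, in line with Table 1.
- Align the cataract criterion in 6.2 and the withdrawal assessments in 5.6 with the chosen time point.
- In 4.8, make clear that participants learn their assignment only after the month-36 visit, keeping the existing provisions for explant and for medically necessary unmasking.
- Keep 0.084 arcminutes as the two-year sizing basis, which SAP 3.1.2 and 3.1.5 already state. In protocol 6.4, stop calling 24 months the study period.

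No extra reporting of early leavers is needed, because SAP 4.2 and 6.1 already cover discontinuation, withdrawal and loss to follow-up.

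The cost is a wording amendment to the Protocol Summary and sections 2.3, 4, 4.1, 4.8, 5.6, 6.1, 6.2, 6.3 and 6.4. If 36 months is chosen, the SAP's time point stays as it is. No visits are added, because Table 1 already schedules month 36.
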